12. ASSESSMENT OF SAFETY

12.1 Adverse Events

12.1.1 Definitions

An AE is defined as any untoward medical occurrence in a subject administered an IP that does not necessarily have a causal relationship with the treatment. An AE can therefore be any unfavorable and unintended sign (eg, an abnormal laboratory finding), symptom (eg, rash, pain, discomfort, fever, dizziness, etc.), disease (eg, peritonitis, bacteremia, etc.), or outcome of death temporally associated with the use of an IP, whether or not considered causally related to the IP.

12.1.1.1 Serious Adverse Event

An SAE is defined as an untoward medical occurrence that at any dose meets one or more of the following criteria:

- Outcome is fatal/results in death (including fetal death)
- Is life-threatening – defined as an event in which the subject was, in the judgment of the investigator, at risk of death at the time of the event; it does not refer to an event that hypothetically might have caused death had it been more severe.
- Requires inpatient hospitalization or results in prolongation of an existing hospitalization – inpatient hospitalization refers to any inpatient admission, regardless of length of stay.
- Results in persistent or significant disability/incapacity (ie, a substantial disruption of a person's ability to conduct normal life functions)
- Is a congenital anomaly/birth defect
- Is a medically important event – a medical event that may not be immediately life-threatening or result in death or require hospitalization but may jeopardize the subject or may require medical or surgical intervention to prevent one of the other outcomes listed in the definitions above. Examples of such events are:
 - Intensive treatment in an emergency room or at home for allergic bronchospasm, blood dyscrasias, or convulsions that do not result in hospitalization, or development of drug dependence or drug abuse
 - Reviewed and confirmed seroconversion for HIV, hepatitis A virus, hepatitis B virus, hepatitis C virus, hepatitis E virus or parvovirus B19

Uncomplicated pregnancies, following maternal or paternal exposure to IP, are not considered an (S)AE; however, any pregnancy complication or pregnancy termination by therapeutic, elective or spontaneous abortion shall be considered an SAE.

12.1.1.2 Suspected Unexpected Serious Adverse Reaction (SUSAR)

Any suspected adverse reaction to study treatment (ie, including active comparators) that is both serious and unexpected.

The event(s) must meet all of the following:

- Suspected adverse reaction
- Serious
- Unexpected
- Assessed as related to study treatment

Once determined to meet the criteria for a SUSAR, an SAE should be submitted to regulatory agencies expeditiously.

12.1.1.3 Non-Serious Adverse Event

A **non-serious** AE is an AE that does not meet the criteria of an SAE.

12.1.1.4 Unexpected Adverse Events

An unexpected AE is an AE whose nature, severity, specificity or outcome is not consistent with the term, representation or description used in the Reference Safety Information. “Unexpected” also refers to the AEs that are mentioned in the IB or prescribing information as occurring with a class of drugs or as anticipated from the pharmacological properties of the product, but are not specifically mentioned as occurring with the particular product under investigation. The expectedness of AEs will be determined by the sponsor using the IB and prescribing information as the Reference Safety Information. This determination will include considerations such as the number of AEs previously observed, but not on the basis of what might be anticipated from the pharmacological properties of a product.

12.1.1.5 Preexisting Diseases

Preexisting diseases that are present before entry into the study are described in the medical history, and those that manifest with the same severity, frequency, or duration after IP exposure, will not be recorded as AEs. However, when there is an increase in the severity, duration or frequency of a preexisting disease after IP exposure, the event must be described on the AE CRF.

For medical events occurring between study entry and IP exposure, see Section 12.3 Untoward Medical Occurrences.

12.1.2 Assessment of Adverse Events

For the purposes of this study, changes in the severity or duration of GvHD experienced after the first IP exposure are collected as an efficacy endpoint and thus are not reportable on the AE CRF, nor will they be included in the analysis of AEs.

Symptoms or diagnostic findings of GvHD, such as skin rashes, abnormal liver function tests, diarrhea, ileus and bowel perforation, should be collected on the AE CRF only if there is an increase in the severity, duration or frequency AND if they begin after first exposure to IP.

All other AEs from the first IP exposure until study completion will be described on the AE CRF using the medical diagnosis (preferred), or, if no diagnosis could be established at the time of reporting the AE, a symptom or sign, in standard medical terminology in order to avoid the use of vague, ambiguous, or colloquial expressions (see definition in Section 12.1). Each AE will be evaluated by the investigator for:

- Seriousness as defined in Section 12.1.1.1
- Severity as defined in Section 12.1.2.1
- Causal relationship to IP exposure or study procedure as defined in Section 12.1.2.2

For each AE, the outcome (ie, recovering/resolving, recovered/resolved, recovered/resolved with sequelae, not recovered/not resolved, fatal, unknown) and if applicable action taken (ie, dose increased, dose not changed, dose reduced, drug interrupted, drug withdrawn, not applicable or unknown) will also be recorded on the AE CRF. Recovering/resolving AEs will be followed until resolution or 30 days after the study completion/termination visit, whichever comes first. The follow-up information will be documented in the AE CRF. If the severity rating for an ongoing AE changes before the event resolves, the original AE report will be revised (ie, the event will not be reported as separate AE). During the course of any AE, the highest severity rating will be reported.

Deviations from protocol-specified procedures of IMP use such as overdosing, underdosing, withdrawal, omission, incorrect route of administration, and use of a product other than the IMP, standard care of the underlying disease or treatment of a TEAE shall be recorded in the Protocol Deviation Form.

Any pregnancy that occurs after administration of IP will be reported on a Pregnancy Report Form.

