10.6 Subject Completion/Discontinuation

A subject is considered to have completed the study when he/she ceases active participation in the study according with the protocol (with or without protocol deviations).

Reasons for completion/discontinuation will be reported on the Completion/Discontinuation CRF, including: completed, screen failure, AE (eg, death), discontinuation by subject (eg, lost to follow-up [defined as 3 documented unsuccessful attempts to contact the subject], dropout), physician decision (eg, pregnancy, progressive disease, non-compliance with IP/protocol violation(s), recovery), study terminated by sponsor, or other (reason to be specified by the investigator, eg, technical problems). Regardless of the reason, all data available for the subject up to the time of completion/discontinuation through the study follow-up period should be recorded on the appropriate CRF.

Every effort will be made to have discontinued subjects complete the study completion/termination visit. If the study completion/termination visit is done as an additional, unscheduled visit, the assessment results shall be recorded with the study completion/termination visit. If a subject terminates participation in the study and does not return for the study completion/termination visit, their last recorded assessments shall remain recorded with their last visit. The reason for discontinuation will be recorded, and the data collected up to the time of discontinuation will be used in the analysis and included in the clinical study report. If additional assessments are required, the assessments shall be recorded separately. Assessments to be performed at the study completion/termination visit (including in cases of withdraw or discontinuation) can be found in Supplement 20.2 Schedule of Study Procedures and Assessments.

Subjects who discontinue study treatment prior to Day 28 will complete the Day 28 visit on Day 28 (± 1 day). If at least 2 weeks have passed since the last dose of study treatment, the Day 28 visit will serve as the study completion/termination visit. If Day 28 is less than 2 weeks following the last dose of study treatment, subjects will complete the Day 28 visit and then the study completion/termination visit 2 weeks (± 1 day) after the last dose of study treatment. In this event, the study completion/termination visit will consist of an office visit with the same assessments as the Day 365 visit.

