Subjects who discontinue study treatment after Day 28 will complete the study completion/termination visit as an office visit 2 weeks (± 1 day) after the last dose of study treatment. Subjects who withdraw from the study after Day 56 will be encouraged to complete the study completion/termination visit at the time of discontinuation. In the event that it is not feasible for the subject to visit the site at the study completion/termination visit after Day 56, the visit may be conducted with a phone call.

Subjects who discontinue study treatment will not attend any other subsequent visits other than Day 28 and the study completion/termination visit (if applicable), except as needed for follow-up of recovering/resolving AEs (see Section 12.1.2).

In the event of subject discontinuation due to an AE, clinical and/or laboratory investigations that are beyond the scope of the required study observations/assessments may be performed as part of the evaluation of the event. These investigations will take place under the direction of the investigator in consultation with the sponsor, and the details of the outcome may be reported to the appropriate regulatory authorities by the sponsor.

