12.7.3.2 Assessment of Abnormal Laboratory Values

For each abnormal laboratory value, the investigator will determine whether the value is considered clinically significant or not. For clinically significant values, the investigator will indicate if the value constitutes a new AE (see definition in [Section 12.1](#)) or if the value is related to a previously recorded AE. Any clinically significant abnormal laboratory finding associated with a pre-existing condition (described in [Section 12.1.1.5](#)) or GvHD will not constitute an AE, unless judged by the investigator to be more severe than expected for the subject's condition. The investigator will also record the severity grading (only if 3 or 4) within the respective laboratory page of the eCRF for a clinically significant laboratory value that constitutes an AE, and the severity grades for the sign, symptom or medical diagnosis in the AE page of the eCRF. Regarding clinically significant abnormal laboratory values that are adverse events, only the highest severity grading will be reported in the eCRF. Regardless of the severity grade, an AE will be followed until resolution or until no longer deemed necessary by the investigator.

If the abnormal value was not clinically significant, the investigator will indicate the reason, ie due to periodic variation, due to a lab error, or due to another issue that will be specified. Additional tests and other evaluations required to establish the significance or etiology of an abnormal value, or to monitor the course of an AE should be obtained when clinically indicated. Any abnormal value that persists should be followed at the discretion of the investigator.

Regarding laboratory abnormal values that are adverse events, only the highest grading will be reported in the eCRF. Regardless of the grade, the AE will be followed until resolution or until no longer deemed necessary by the investigator.

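### AE follow-up after the termination visit is stated only for recovering/resolving events, not for unresolved ones, and Section 12.7.3.2 gives a different end point

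*Protocol*

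**What the plan says.** Protocol Section 12.1.2 gives six AE outcomes: "recovering/resolving, recovered/resolved, recovered/resolved with sequelae, not recovered/not resolved, fatal, unknown". An event that is improving and one that is not are therefore recorded under different codes. The rule for what happens after the last visit names only the improving kind: "Recovering/resolving AEs will be followed until resolution or 30 days after the study completion/termination visit, whichever comes first".

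Section 10.6 limits subjects who stop study treatment to the Day 28 visit and, if it is separate, the termination visit, "except as needed for follow-up of recovering/resolving AEs". Footnote a of Tables 1 and 2 carries the same exception. The corresponding footnotes in SAP Sections 14.2 and 14.3 do so too.

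Section 12.7.3.2, on abnormal laboratory values, says: "Regardless of the severity grade, an AE will be followed until resolution or until no longer deemed necessary by the investigator". A near-identical sentence closes that section: "Regardless of the grade, the AE will be followed until resolution or until no longer deemed necessary by the investigator". Neither sentence restricts follow-up by outcome code or caps it at 30 days.

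**The concern.** Taken literally, the rule favours the less worrying events. An AE on its way to recovery is tracked for up to 30 days after termination; one that is unchanged or getting worse has no stated follow-up from that visit on. Unresolved AEs are the ones whose final outcome is least certain, so they are where follow-up adds most information.

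The subjects affected are mainly those who stop treatment early, because their termination visit comes soon after dosing. For such a subject an AE coded as not resolved at that visit may simply stay so coded, whatever happens next. Outcome data, including fatal outcomes, may then be incomplete in the subjects who tolerated or responded to treatment least well. A site reading Section 12.7.3.2 would also apply a different stopping point from a site reading Section 12.1.2.

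**Working it through.** The plan states no figure to reproduce. The check sets the texts side by side and does day arithmetic on nominal visit days.

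**Do the texts agree?**
- Section 12.1.2: covers recovering/resolving AEs; ends at resolution or 30 days after termination.
- Section 10.6 and footnote a of Tables 1 and 2: same scope; Section 10.6 refers back to 12.1.2.
- Section 12.7.3.2: no limit by outcome code; ends at resolution or at the investigator's discretion.

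There are two readings of 12.7.3.2. If it covers only laboratory-based AEs, those AEs have two end points and all other unresolved AEs have no stated follow-up after termination. If it covers every AE, unresolved events are followed, but the text contradicts 12.1.2, 10.6 and the footnotes. No passage says which prevails. The gap and a general contradiction cannot both hold, but either reading needs correction.

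**How early is termination?** Inputs:
- If treatment stops before Day 28 and at least 2 weeks have passed since the last dose, "the Day 28 visit will serve as the study completion/termination visit" (Section 10.6).
- Otherwise, for early stoppers, termination is 2 weeks (±1 day) after the last dose (Section 10.6).
- Completers take their last dose on Day 49 and finish on Day 365 (Table 1).
- The treatment-emergent window is 30 days after the last dose (SAP Section 8.2).

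With last dose on Day L:
- early stopper's termination T = the later of Day 28 and L + 14
- latest follow-up of a recovering/resolving AE = T + 30
- treatment-emergent window closes on L + 30
- part of that window left after termination = (L + 30) − T

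| Last dose | Termination T | Recovering AE followed to (T + 30) | Days stated in 12.1.2 for unresolved AE after T | Window closes (L + 30) | Window left after T |
|---|---|---|---|---|---|
| Day 6 | Day 28 | Day 58 | 0 | Day 36 | 8 days |
| Day 14 | Day 28 | Day 58 | 0 | Day 44 | 16 days |
| Day 21 | Day 35 | Day 65 | 0 | Day 51 | 16 days |
| Day 49, completer | Day 365 | Day 395 | 0 | Day 79 | none |

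When termination is 14 days after the last dose, 30 − 14 = 16 days remain, or 15 to 17 with the ±1 day visit window. If the last dose is before Day 14, termination stays at Day 28 and less of the window remains. For completers, termination comes 365 − 49 = 316 days after the last dose.

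The treatment-emergent window classifies AEs by onset. It serves here only as a yardstick for the period the SAP still counts as related in time to treatment.

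**Is there later contact?** Under Section 10.6, a stopper who terminates on Day 28 has no scheduled visit in the 365 − 28 = 337 days to Day 365. Under Section 8.2, all subjects are followed at Days 100, 180 and 365. The two sections disagree.

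**The case against.** The best defence is that the rest of the protocol narrows the gap.

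- A reader might infer that unresolved AEs get no follow-up at all. The documents do not support that. Section 12.1.2 also says "All other AEs from the first IP exposure until study completion will be described on the AE CRF", with outcome recorded and severity revised while an event is ongoing. The gap opens only after the termination visit.
- A reader might infer that later deaths are certain to be missed. That is also too strong. Section 11.12 collects date and cause of death at the Table 1 visits through Day 365, Section 8.2 keeps all subjects in follow-up, and Section 2 requires SAE reports within 24 hours of awareness with no stated end date. These safeguards are weaker for early stoppers: Section 10.6 removes the visits at which deaths would be collected, and the 24-hour rule works only if the site hears of the event.
- A reader might cite the liver failure and bowel perforations in the earlier steroid-refractory GvHD study (Section 6.4.2). They are reported by time of occurrence and are not shown to be AEs already open at a termination visit. The perforation at 2 months also falls beyond 14 + 30 = 44 days after the last dose. They do not measure this gap.
- The restriction may be a slip for *ongoing*, a word Section 12.1.2 itself uses nearby. That is plausible, but the restriction appears in several places and sites would follow the words as printed.
- The practical effect is small. SAP Section 1 reports that the study closed with one subject, treated under the original protocol, and that only listings are planned.

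The first, second and last points limit the size of the finding. None makes the stated rule correct.

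**Conclusion.** The point holds as a faulty and inconsistent follow-up rule, not as proof of lost deaths. Section 12.1.2, Section 10.6 and footnote a of Tables 1 and 2 omit the *not recovered/not resolved* category from follow-up after termination. Section 12.7.3.2 sets a different end point, which conflicts at least for laboratory-based AEs.

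For early treatment stoppers, the final outcome of an unresolved AE, including a fatal one, can be missed. The difference in stated follow-up is up to 30 days per event. Where termination is 2 weeks after the last dose, about 16 days of the SAP's treatment-emergent window remain at that visit. For Day 365 completers the consequence is slight.

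This rests on 12.7.3.2 being confined to laboratory AEs and on 10.6 governing stoppers' visits. If 12.7.3.2 covers all AEs, the gap closes and the contradiction remains; if Section 8.2 governs, later visits would pick up many outcomes. The documents do not give the share of AEs unresolved at termination, so the number affected cannot be estimated. With one subject enrolled, this is a defect of the protocol text with little effect on the data.

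**What to change.** In Section 12.1.2, Section 10.6 and footnote a of Tables 1 and 2, replace the reference to recovering/resolving AEs with *all AEs ongoing at the study completion/termination visit (recovering/resolving or not recovered/not resolved)*. Keep the existing 30-day limit for recording the outcome. Reconcile both sentences in Section 12.7.3.2 with that text, so that one end point applies to laboratory-based AEs.

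Separately, reconcile Section 10.6 with Section 8.2 on whether subjects who stop treatment are followed at Days 100, 180 and 365. The 30-day wording does not settle that question, and it would not capture AEs that begin after termination.

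The cost is a wording amendment and a few extra follow-up contacts for AEs still open at termination. Sample size and the efficacy analyses are unaffected.

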12.1.2.1 Severity

The investigator will assess the severity of each AE using his/her clinical expertise and judgment based on the National Cancer Institute Common Terminology Criteria for Adverse Events (NCI CTCAE) version 4.03. In the event an AE is not described in the NCI CTCAE version 4.03, the severity grades will be mapped to the terms listed in [Table 3](#). For assessing the severity of AEs resulting from laboratory values, see section [12.7.3.2](#).

These severity definitions will also be used to assess the severity of an AE with a study-related procedure(s), if necessary.

12.1.2.2 Causality

Causality is a determination of whether there is a reasonable possibility that the IP is etiologically related to/associated with the AE. Causality assessment includes, eg, assessment of temporal relationships, dechallenge/rechallenge information, association (or lack of association) with underlying disease, presence (or absence) of a more likely cause and physiological plausibility. For each AE, the investigator will assess the causal relationship between the IP and the AE using his/her clinical expertise and judgment according to the following most appropriate algorithm for the circumstances of the AE:

- Not related (both circumstances must be met)
 - Is due to underlying or concurrent illness, complications, concurrent treatments or effects of concurrent drugs
 - Is not associated with the IP (ie, does not follow a reasonable temporal relationship to the administration of IP or has a much more likely alternative etiology)
- Unlikely related (either 1 or both circumstances are met)
 - Has little or no temporal relationship to the IP
 - A more likely alternative etiology exists
- Possibly related (both circumstances must be met)
 - Follows a reasonable temporal relationship to the administration of IP
 - An alternative etiology is equally or less likely compared to the potential relationship to the IP

- Probably related (both circumstances must be met)
 - Follows a strong temporal relationship to the administration of IP, which may include but is not limited to the following:
 - Reappearance of a similar reaction upon re-administration (positive rechallenge)
 - Positive results in a drug sensitivity test (skin test, etc.)
 - Toxic level of the IP as evidenced by measurement of the IP concentrations in the blood or other bodily fluid
 - Another etiology is unlikely or significantly less likely

For events assessed as not related or unlikely related and occurring within 1 week of study treatment administration, the investigator shall provide the alternative etiology. These causality definitions will also be used to assess the relationship of an AE with a study-related procedure(s), if necessary.

12.2 Urgent Safety Measures

An urgent safety measure is an immediate action taken, which is not defined by the protocol, in order to protect subjects participating in a clinical trial from immediate harm. Urgent safety measures may be taken by the sponsor or clinical investigator and may include any of the following:

- Immediate change in study design or study procedures
- Temporary or permanent halt of a given clinical trial or trials
- Any other immediate action taken in order to protect clinical trial participants from immediate hazard to their health and safety

The investigator may take appropriate urgent safety measures in order to protect subjects against any immediate hazard to their health or safety. The measures should be taken immediately and may be taken without prior authorization from the sponsor. In the event(s) of an apparent immediate hazard to the subject, the investigator will notify the sponsor immediately by phone and confirm notification to the sponsor in writing as soon as possible, but within 1 calendar day after the change is implemented. The sponsor will also ensure the responsible ethics committee(s) (EC(s)) and relevant competent authority(s) are notified of the urgent safety measures taken in such cases according to local regulations.

